A multidisciplinary intervention in total knee arthroplasty - a multicenter, randomized controlled trial in osteoarthritis patients (MULTI-KNEE trial).

This is a protocol for a multicenter, three-armed, randomized controlled trial (RCT). An estimated one in five patients undergoing total knee arthroplasty (TKA) does not improve in pain and function, suggesting that among the 6466 patients who underwent primary TKA in Norway in 2016, more than 1200 patients derived little or no benefit from the surgery and continue to experience chronic pain. In addition, these numbers suggest that more than 100 000 000 NOK are spent every year on an invasive treatment with questionable effect⁽¹⁾. This study will evaluate the effect of a multidisciplinary intervention delivered either as a substitute, or in addition to, TKA for patients identified as being at risk for non-improvement after TKA.

Hypotheses, aims and objectives

The overall aim of this study is to test the effectiveness of a 12-week integrated Physiotherapy (PT) group exercise program in combination with cognitive behavioral therapy (CBT) support, delivered by physiotherapists, in patients with knee osteoarthritis (OA) who are on a waiting list for TKA and who are identified as being at risk for non-improvement based on a set of preoperative criteria. The effects of the integrated PT exercise program and CBT will be evaluated both as a substitute for TKA and as a supplement to TKA in comparison to TKA alone. We hypothesize that for patients identified as being at risk for postoperative non-improvement: 1) the effect of PT exercise and CBT alone will be equivalent to surgical treatment alone, and 2) the effect of PT exercise and CBT in combination with surgical treatment will be better than surgical treatment alone. The effects of the three treatments will be evaluated in terms of pain relief (primary outcome), functioning and quality of life (QOL) (secondary outcomes) at 12-month follow-up. The study includes a pilot study with 15 participants prior to the full-scale study.

This large study consists of four sub-studies and a pilot study, each with individual aims.

The pilot study has the following aims:

- To evaluate the feasibility of the multidisciplinary intervention alone and as a supplement to TKA
- To evaluate the rate of recruitment, patients' willingness to participate and adherence to the intervention
- Investigate patients' experiences with participation in the study

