All patients scheduled for TKA at the two surgical clinics (i.e., Lovisenberg Diaconal Hospital (Lovisenberg), Kysthospitalet Hagevik (Hagevik)) will be screened prior to their consultation with their orthopedic surgeon. The screening will be performed using a validated prioritization algorithm developed by Escobar and Riddle⁽⁷⁻⁹⁾, using the following preoperative predictors: preoperative pain and function; presence of widespread pain; and the following additional factors: anxiety/depression; pain catastrophizing; coping strategies. The additional predictors were selected based on findings from our previous studies^(10, 11) and the literature⁽¹²⁾. Based on this screening, each patient will be categorized as either inappropriate/inconclusive, or appropriate for surgery. The surgeon and patient will be blinded to the result of the screening during the consultation. The surgeon will receive a sealed envelope with the result of the screening. After the surgeon and the patient have jointly decided to schedule the patient for TKA, the surgeon will open the envelope. Patients categorized as inconclusive/inappropriate will be invited to participate in the study. Patients who consent to participate will then be randomly allocated to one of the intervention groups or the control group using allocation numbers in sealed envelopes. The envelopes will be prepared before initiation of the trial by an independent staff member, and distributed to the two study sites (Lovisenberg and Hagevik). The envelopes will be kept in a locked location only available to the research assistants at each study site. Reasons for not participating will be recorded.

Figure 2 – allocation of patients into 3 treatment arms

Patients who meet the following inclusion criteria will be eligible for the study: 1) scheduled for TKA for OA at Lovisenberg or Kysthospitalet Hagevik, Bergen, 2) Charnley comorbidity classification A, B or C, 3) ASA grade 1 and 2, and 4) BMI<40, 5) able to read and write in Norwegian. In addition, the patient must be identified as being at high risk for an unsuccessful outcome after TKA based on cutoff scores on 2 or more of the following screening criteria, whereof one must be within the physical components, and one must be within the psychological components of the screening criteria:

- Age <55 years
- Preoperative pain and function level: The Knee Injury and OA Outcome Score (KOOS) pain and physical scale combined⁽⁹⁾, cutoff ≤ 22 .

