Adverse events	Patients, physiotherapists, medical records	0, 3, 6, 12 and 24 months
Recruitment, screening, randomization	Flow chart, inclusion and exclusion	0, 3, 6, 12 and 24 months
Retention in study/loss to follow-up	Loss to follow-up, crossover	0, 3, 6, 12 and 24 months

Registry-based data

Use of health care resources: registry data from the KUHR-system (i.e., control and payment of reimbursements to health service providers), the Norwegian Patient Registry (NPR) and FD Trygd social security database. All information will be anonymized and linked to each patient using a unique ID number generated prior the start of this study. Data on revision surgery and deep prosthetic infections will be retrieved from the Norwegian Arthroplasty Registry⁽²⁶⁾.

Other measures

Adherence with AktivA: The physiotherapists will monitor patients' adherence with the AktivA program during the 12 weeks. Adherence will be measured as the total number of the 24 sessions completed. Good compliance will be defined as participation in 75% or more of the exercise sessions, medium compliance will be defined as participation in 50-74% of the sessions, and poor compliance will be defined as participation in less than 50% of the sessions.

Compliance with the e-therapy program: Good adherence to the e-therapy program will be defined as completing 75% of the content; medium compliance will be defined as completing 50-74% of the program, and poor compliance will be defined as completing less than 50% of the sessions. In addition, time used in the program will be assessed.

Power calculation and sample size

The primary outcome measure is KOOS pain subscale, 12-month follow-up. The minimal perceptible clinical improvement (MPCI) for KOOS has been determined to be 10 points⁽¹³⁾ which will be considered a minimal clinically important change. The power will be set to 80%, the level of significance at 1%, and the standard deviation of the measurements considered equal in both groups at 16, resulting in a sample size of 62 patients in each treatment group. The attrition rate will be set to 20% to account for drop-out and crossovers. Therefore, we will include and randomize a total of 230 patients.

Statistical analysis

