Data analyses will be performed using SPSS version 24.0 (IBM, Armonk, NY) and STATA version 14.2. Differences between the intervention and control group will be analyzed using responder analysis based on the OMERACT-OARSI responder criteria^(27, 28). Differences between the intervention and control groups at 12 months will also be analyzed using ANOVA. Non-normally distributed data will be analysed using the Kruskal-Wallis test. Differences over time at 3, 6 and 12 months will be analysed using mixed models for repeated measures to account for dependencies caused by each patient being measured several times. P-values <0.05 will be considered statistically significant, and all estimates will be reported with 95% confidence intervals. Effect sizes will be calculated for group differences using Cohen's coefficient *d*. A *d*-value ≥ 0.40 will be considered a clinically meaningful difference⁽²⁹⁾. All analyses will be performed based on the intention to treat principle.

Economic evaluation

The cost-effectiveness analysis will be based on the Norwegian healthcare system. A societal perspective will be used as recommended by Russel et al⁶⁷. A Markov decision model will form the theoretical framework for a cost-effectiveness analysis to estimate the costs and benefits for patients in the two intervention groups and the control group. With this model, simulation will be performed of long-term health benefits, health care costs and cost-effectiveness of the specified interventions. The main variables will be QALYs based on the EQ5D, combined with use of health care resources and use of medication. The incremental cost-effectiveness ratio (ICER) will be used to summarize the cost-effectiveness of each of the intervention groups, compared to the control group. Sensitivity analyses will be performed to test the stability of the conclusions. According to the literature, a clinically relevant difference in EQ5D between the groups would be 0.08⁶⁸. Keeping alpha to 5% and power to 80%, we would need 42 individuals in each group.

Given we plan to enroll 62 in each group, our study is sufficiently powered to reveal a clinical relevant difference also for this secondary aim.

Timelines

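### A single 20% allowance counts crossovers as lost patients although the analysis is ITT, so the stated power at 1% depends on the crossover share and ITT alone can favour the equivalence hypothesis

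*Protocol*

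**What the plan says.** The Protocol's section on power and sample size takes a 10-point difference in KOOS pain at 12 months and an SD of 16. It continues: "The power will be set to 80%, the level of significance at 1" per cent. This gives 62 per group. One allowance then leads to 230 randomised: "The attrition rate will be set to 20% to account for drop-out and crossovers". No split between the two is given.

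The Statistical analysis section states: "All analyses will be performed based on the intention to treat principle". It also uses a different threshold: "P-values <0.05 will be considered statistically significant".

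The first hypothesis is that "the effect of PT exercise and CBT alone will be equivalent to surgical treatment alone"; the second is that the programme plus TKA is better than TKA alone. The programme "will be evaluated both as a substitute for TKA and as a supplement to TKA". Under Recruitment and allocation, patients are invited only at this point: "After the surgeon and the patient have jointly decided to schedule the patient for TKA". Table 1 lists "Loss to follow-up, crossover" under the feasibility-study outcomes.

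**The concern.** Drop-out and crossover act differently under ITT. A drop-out without a 12-month value reduces the number analysed, and dividing by 0.8 makes up for that. A crossover is still analysed in the randomised arm. If that patient's outcome moves toward the other arm's, the difference itself shrinks, and the division by 0.8 was not built to correct that.

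Two things are at stake. The first is whether 80% power at 1% describes the planned analysis. The second is how the substitute-for-TKA question will be read. Every patient has already agreed with the surgeon to have TKA, so some patients allocated to the programme alone may plausibly go on to surgery. If TKA is the better treatment, such crossover makes the arms look more alike, and likeness is what the first hypothesis predicts. For superiority, dilution under ITT is conservative; for equivalence it is not.

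**Working it through.** **Inputs from the Protocol:** difference 10, SD 16, power 80%, alpha 1% (sample size) and 5% (analysis), 62 per group, 20% allowance, 230 randomised in three arms. **Assumed:** two-sided test, equal arms, allowance fully used, crossover in one of the two compared arms only, crossovers taking the other arm's mean, SD unchanged.

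**Plan's own figure.** A two-sample t-test (noncentral t) at two-sided 1% with 62 per arm has 80.4% power, and 62 is the smallest n reaching 80%. Inflated, 3 × 62 / 0.8 = 232.5, close to 230. Working back, 230 × 0.8 / 3 = 61.3 per arm, so the whole 20% was removed as missing patients.

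**Power under ITT.** Let d be drop-out and c crossover, both as shares of those randomised, with d + c = 20%.

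- Analysed per arm: n = (230/3) × (1 − d)
- Crossover share among those analysed: f = c/(1 − d)
- ITT difference: 10 × (1 − f)

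| c | d | n per arm | f | ITT difference | Power at 1% | Power at 5% |
|---|---|---|---|---|---|---|
| 0% | 20% | 61.3 | 0 | 10.00 | 79.9% | 93.0% |
| 5% | 15% | 65.2 | 0.059 | 9.41 | 77.0% | 91.5% |
| 10% | 10% | 69.0 | 0.111 | 8.89 | 74.1% | 90.0% |
| 15% | 5% | 72.8 | 0.158 | 8.42 | 71.3% | 88.4% |
| 20% | 0% | 76.7 | 0.200 | 8.00 | 68.6% | 86.8% |

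**Sensitivity to the crossover patient's outcome.** If crossovers move only half-way, the difference is 10 × (1 − 0.5f). Power at 1% is then 79.9, 80.0, 80.2, 80.5 and 80.7% down the table, so nothing is lost.

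**Allowance not fully used.** With 10% drop-out and 5% crossover, n = 69.0, f = 0.05/0.90 = 0.056 and the difference is 9.44. Power is 80.2% at 1% and 93.1% at 5%.

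**Which contrasts are affected.** Crossover from the programme-alone arm to TKA touches only comparisons that include that arm. It does not dilute programme plus TKA against TKA alone.

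**Equivalence, illustration only.** The Protocol states no margin or decision rule. Assume a margin of ±10, a true 10-point inferiority of the programme alone, and equivalence declared when the 95% CI lies inside the margin. The true ITT difference is −10 × (1 − f), with n as in the table. Integrating over the variance estimate, the chance of declaring equivalence is about 2.5, 6.0 and 11.7% at 0, 10 and 20% crossover.

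**The case against.** The strongest reply is that the analysis section works at 5%, where one-way crossover never takes power below 86.8%. That stands: the power shortfall exists only at the 1% level used for sizing.

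Second, the crossover most easily foreseen, from the programme alone to TKA, leaves the superiority comparison untouched. For the other comparison the hypothesis is equivalence, so power to detect 10 points is not the power of that hypothesis. This also stands. It moves the weight of the point from power to the equivalence question.

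Third, neither the split nor the crossover patient's outcome is documented. A patient who has surgery late has had the programme and only part of a year after TKA, so full movement to the other arm's mean is not assured. Half-way movement removes the power loss altogether.

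Fourth, supporting analyses are commonly left to an SAP, which is not shown. Their absence is therefore no finding. But the Protocol makes a positive statement that every analysis is ITT, and a crossover analysis in an SAP would conflict with it. The sizing step is in the Protocol itself.

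Fifth, the pilot records crossover and may lead to changes in the protocol. With 15 patients over three arms it cannot fix a rate.

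A reader might infer that the trial is underpowered, or that an equivalence finding would be false. The documents support neither: no crossover rate is given, total losses may stay below 20%, and the false-equivalence figures rest on an assumed margin, rule and true difference.

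**Conclusion.** The point holds in a limited form. One allowance treats two different mechanisms as one, and under ITT it delivers the stated 80% at 1% only if little of a fully used 20% is crossover, or if crossovers keep a good part of their own arm's outcome. With full movement to the other arm's mean, the shortfall grows from about 3 points at 5% crossover to about 11 points at 20% (79.9 to 68.6%). At the 5% threshold there is no shortfall from one-way crossover, so the conflict between 1% and 5% decides whether the power part matters and must be settled first.

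The equivalence part does not depend on that conflict. If TKA is better, patients in the programme-alone arm who receive it move the ITT result toward the hypothesised one, and a rule that all analyses are ITT leaves no analysis to show how far. The direction follows from the design; the size cannot be fixed from the documents.

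**What to change.** Keep 230 patients and keep ITT as the main analysis.

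1. Reconcile the 1% level in the sample-size section with the 5% level in the analysis section.
2. State assumed drop-out and crossover separately, both as shares of those randomised and preferably by arm and with a range. Restate ITT power with the effect 10 × (1 − c/(1 − d)) at the reconciled level. An example, with placeholder rates: with 10% drop-out and 5% crossover, power is 80.2% at 1% and 93.1% at 5%.
3. Amend the statement that all analyses are ITT, so that the programme-alone versus TKA equivalence result is reported beside one pre-specified supporting analysis that accounts for crossover. Per-protocol and complier-average analyses are both options. State the assumption made: a programme-alone patient who later has TKA may resemble the combined arm more than the TKA arm, which weakens a complier-average estimate.
4. Accompany any claim of equivalence with the share of the programme-alone arm that received TKA by 12 months. The planned Norwegian Patient Registry data may supply this.

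The cost is wording, one further analysis and one reported item, with no extra patients. The downside is a slightly less favourable stated power and a less precise supporting estimate. At 10% drop-out and 10% crossover the ITT 95% CI half-width is about 5.4 points. A complier-average estimate, treating f as known, has about 5.39 / (1 − 0.111) = 6.1.

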The primary outcome will be the pain subscore from the KOOS at 12 months. The KOOS is a knee joint specific questionnaire developed in 1998 for the purpose of evaluating short-term and long-term symptoms and functioning in subjects with knee injury and OA. KOOS is a 42-item survey designed to assess people's opinions about the difficulties they experience with activity due to problems with their knees during the past week. Each of the 42 items carries equal weighting (0–4), with higher scores indicating better outcomes. KOOS has 5 subscales: pain, other symptoms, activities of daily living (ADL), function in sport and recreation, and knee-related QOL. Scores are transformed to a 0-100 scale, with 0 representing extreme knee problems and 100 representing no problems. The KOOS has been validated for use in TKA and has been shown to be a valid, reliable and responsive measure⁽¹³⁾.

Secondary outcomes will include the 4 remaining KOOS subscales and the following additional measures:

Patient-reported outcomes

Pain intensity and interference with functioning: the Brief Pain Inventory⁽¹⁴⁾.

Sleep quality: the Pittsburgh Sleep Quality Index (PSQI)⁽¹⁵⁾.

Pain Catastrophizing: the Pain Catastrophizing Scale (PCS)⁽¹⁶⁾.

Pain-related fear of movement: the Fear-Avoidance Belief Questionnaire (FABQ)⁽¹⁷⁾.

Mood states (depression and anxiety): the Hospital Anxiety and Depression Scale (HADS)⁽¹⁸⁾.

Health-related quality of life (HRQoL): EuroQol-5D-3L (EQ-5D-5L)⁽¹⁹⁾.

The Health Locus of Control Scale (HLCS) will be used to measure patients' anticipations between own health and disease behavior and consequences of the behavior⁽²⁰⁾.

The Forgotten Joint Score will be used to assess how natural the prosthesis feels after TKA⁽²¹⁾.

Anchor measures: Patient acceptable symptom state, treatment failure, global perceived effect.

Clinical assessments

Knee functioning: the new American Knee Society Score (AKSS)⁽²²⁾.

Comorbidity will be measured with the Self-Administered Comorbidity Questionnaire (SCQ-19)⁽²³⁾.

Time in activity, number of steps: ActivePal Professional single-axis accelerometer⁽²⁴⁾.

Functional lower extremity strength: the 30-second sit to stand test⁽²⁵⁾.

Walking speed will be measured using the 6 minutes walk test.

Radiological assessments

X-rays including weightbearing AP, lateral view, Rosenberg view and long leg weightbearing AP view (HKA), preoperative and at 24 months. OA grading according to Kellgren-Lawrence and Ahlbachs⁽⁴³⁾.

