Table 1 study measures

Construct assessed	Data collection instrument	Time of collection
Primary outcome measure	Proms	
Pain	Pain subscale of the KOOS	0, 3, 6, 12 and 24 months
Secondary outcome measures	Data collection instrument	Time of collection
	Proms	
Pain, symptoms, ADL, QOL, sport & recreation	The five individual subscales of the KOOS	0, 3, 6, 12 and 24 months
Self-reported level of physical activity	HUNT2, Stages of Change physical activity	0, 3, 6, 12 and 24 months
Co-morbidity	The Self-Administered Co-Morbidity Questionnaire	0 months
Pain, interference with functioning, number of painful sites	Brief pain inventory	0, 3, 6, 12 and 24 months
Sleep	Pittsburgh Sleep Quality Index	0, 3, 6, 12 and 24 months
Catastrophic thinking related to pain	Pain Catastrophizing scale	0, 3, 6, 12 and 24 months
Locus of control	The Health Locus of Control Scale	0, 3, 6, 12 and 24 months
Pain-related fear of movement	The Fear-Avoidance Belief Questionnaire	0, 3, 6, 12 and 24 months
Mood states	The Hospital Anxiety and Depression Scale	0, 3, 6, 12 and 24 months
Health-related quality of life	EuroQol-5 (EQ5D-5L)	0, 3, 6, 12 and 24 months
Natural feeling of joint	Forgotten Joint Score	0, 3, 6, 12 and 24 months
Anchor measures of satisfaction	Patient acceptable symptom state	0, 3, 6, 12 and 24 months
	Treatment failure	0, 3, 6, 12 and 24 months
	Global perceived effect	0, 3, 6, 12 and 24 months
	Objective measures	
Functional lower extremity test	The 30 second sit to stand test	0, 3, 6, 12 and 24 months
Walking	6 minutes walk test	0, 3, 6, 12 and 24 months
Body mass index	Weight from baseline to follow-up	0, 3, 6, 12 and 24 months
Time in active position/number of steps	The ActivePal Professional Single Axis accelerometer	0, 3, 6, 12 and 24 months
Radiological measurements	Weightbearing AP, lateral view, Rosenberg view and long leg weightbearing AP view (HKA)	0 and 24 months
Other measurements		
Adverse events	Physiotherapy-reported, patient-reported, medical records	0, 3, 6, 12 and 24 months
	Registry-based data	
Use of health care resources	The KUHR-system	0, 3, 6, 12 and 24 months
	The Norwegian Patient Registry	0, 3, 6, 12 and 24 months

	FD trygd social security data base	0, 3, 6, 12 and 24 months
Outcomes, Feasibility study		
Adherence to intervention	Records, physiotherapists. Data, eTherapy.	0, 3, 6, 12 and 24 months
Acceptability of the intervention	Questionnaires, interviews	0, 3, 6, 12 and 24 months

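### The 12-month KOOS pain comparison is planned as an ANOVA with no baseline term, switching to Kruskal-Wallis for non-normal data, although month-0 scores and a mixed model are already in the plan

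*Protocol*

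**What the plan says.** The Primary outcome section states: "The primary outcome will be the pain subscore from the KOOS at 12 months". Table 1 lists "Pain subscale of the KOOS" at months 0, 3, 6, 12 and 24, so a baseline value of the primary outcome is collected.

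The Statistical analysis section first names a responder analysis. It then continues: "Differences between the intervention and control groups at 12 months will also be analyzed using ANOVA". No covariate is mentioned. The next two sentences are "Non-normally distributed data will be analysed using the Kruskal-Wallis test" and "Differences over time at 3, 6 and 12 months will be analysed using mixed models for repeated measures". The section also promises: "P-values <0.05 will be considered statistically significant, and all estimates will be reported with 95% confidence intervals".

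The section on power and sample size takes its target difference from this statement: "The minimal perceptible clinical improvement (MPCI) for KOOS has been determined to be 10 points". It sets power at 80% with "the level of significance at 1%, and the standard deviation of the measurements considered equal in both groups at 16", and arrives at 62 patients per group.

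**The concern.** Two features of the 12-month comparison are fixed in a way that can be improved at almost no cost.

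- **No baseline term.** An ANOVA of 12-month scores leaves in the error term whatever variation baseline KOOS pain could explain. It also leaves any chance baseline imbalance in the estimated difference. The mixed model does not fill this gap as written, because the Protocol assigns it to change over time and gives it no baseline term.
- **A switch driven by the data.** The Kruskal-Wallis sentence is general, sets no criterion for non-normality, and follows directly on the ANOVA sentence. KOOS pain is bounded at 0 and 100, so a skewed 12-month distribution is plausible and the switch could be triggered for the primary outcome. Kruskal-Wallis is an omnibus rank test. It cannot adjust for baseline, and it gives no mean difference with a 95% CI to set against the 10 points used for sample size.

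The stake is precision and readability of the main result, not bias. An interval estimate matters more than usual here because one of the two hypotheses is that the exercise and CBT programme alone is equivalent to surgery, and equivalence is judged from the interval for a difference.

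**Working it through.** **Inputs from the Protocol.** Difference 10 points, SD 16, 62 per group, power 80%, level 1% (power and sample size section); level 5% (Statistical analysis section). Sidedness is not stated; I take it as two-sided.

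**Assumptions.** The correlation r between baseline and 12-month KOOS pain is not given; I use 0.2, 0.3 and 0.5. For the imbalance calculation, baseline SD is also taken as 16. Each contrast is treated as a two-group comparison.

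**Step 1: reproduce the Protocol's figure.** A two-sided two-sample t-test at 1%, difference 10 and SD 16, by the noncentral t distribution, gives 80.4% power at 62 per group, and 62 is the smallest n reaching 80%. The normal approximation gives 60. So 62 per group is an unadjusted calculation on the raw SD.

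**Step 2: effect of baseline adjustment.**

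- Residual SD = 16 × √(1 − r²); the variance falls by r².
- SE of the difference = residual SD × √(2/62). Unadjusted: 16 × √(2/62) = 2.87.
- 95% CI half-width = t × SE, with 122 degrees of freedom (121 adjusted).
- Power from the noncentral t with noncentrality 10/SE.

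| r | Variance reduction | Residual SD | 95% CI half-width | Power at 1% | Power at 5% | n per group for 80% power at 1% |
|---|---|---|---|---|---|---|
| 0 (unadjusted) | 0% | 16.00 | 5.69 | 80.4% | 93.2% | 62 |
| 0.2 | 4% | 15.68 | 5.57 | 82.3% | 94.1% | 60 |
| 0.3 | 9% | 15.26 | 5.43 | 84.7% | 95.1% | 57 |
| 0.5 | 25% | 13.86 | 4.93 | 91.7% | 97.9% | 47 |

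The last column only expresses the gain in patients; no smaller trial is proposed.

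**Step 3: chance baseline imbalance.** The standard error of the baseline difference between two arms is 16 × √(2/62) = 2.87 points. With equal SDs, an imbalance of one standard error shifts the unadjusted 12-month difference by r × 2.87: 0.57, 0.86 and 1.44 points for r = 0.2, 0.3 and 0.5. Adjustment removes this shift.

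**Step 4: the rank-test branch.** No arithmetic is needed. The Statistical analysis section promises estimates with 95% CIs, and the sample size rests on a difference in KOOS points. If KOOS pain is judged non-normal, the named replacement supplies neither a difference in points nor an interval. This holds whatever r is.

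**The case against.** The strongest reply is that the Protocol does not forbid a baseline covariate: it simply does not mention one, and a statistical analysis plan could add it. The ANOVA is valid, and the sample size was calculated for an unadjusted comparison, so design and analysis agree. The gain rests on an assumed r, and r may be low: eligibility depends partly on a low combined KOOS pain and function score, which could narrow the baseline range. At r of 0.2 to 0.3 the CI half-width shrinks by only 0.1 to 0.3 points, and at the 5% level power is already 93%. The ANOVA is not named as the primary analysis, and the mixed model could still supply a 12-month difference with an interval if the rank test were used.

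Much of this stands as a limit on size. The precision gain is uncertain and may be small, and validity is not in question. It does not remove the point. The Protocol is not silent on method: it names the 12-month analysis and its replacement, so an analysis plan would have to depart from that text. The mixed model could help only if it were given a baseline term and an explicit 12-month contrast, and the Protocol gives it neither. The switch to Kruskal-Wallis is stated text and does not depend on r.

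**Conclusion.** The concern holds. The planned 12-month comparison is a valid test of difference but uses less information than the trial collects, and its form can change after the data are seen. For assumed r from 0.2 to 0.5, leaving out baseline costs between about 0.1 and 0.8 points of 95% CI half-width. It costs about 2 to 11 percentage points of power at the 1% level, or about 1 to 5 at the 5% level. These figures rest on SD 16, 62 per group, a two-group approximation and an r that the Protocol does not give. The second half of the point needs no assumption about r: under the Kruskal-Wallis branch, that analysis has no KOOS-point difference and no interval to compare with 10 points. This should be fixed because the remedy is nearly free, not because the trial's conclusions would otherwise be invalid.

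**What to change.** For KOOS pain, name the already planned mixed model over 3, 6 and 12 months as the primary analysis, with arm-by-visit terms and baseline KOOS pain. A term for site (the two hospitals) is a reasonable optional addition. Report the two 12-month contrasts against TKA alone, in KOOS points with 95% CIs, whatever the distribution. Keep the ANOVA, Kruskal-Wallis and the responder analysis as secondary or sensitivity analyses.

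The cost is a change of wording in the Statistical analysis section, with no new data and no new patients. The model also uses patients who have a 3- or 6-month score but no 12-month score. Its one downside is that it relies on a missing-at-random assumption for them, against which the retained ANOVA serves as a sensitivity check. The change does not by itself settle the equivalence hypothesis, which also needs a margin; that is a separate matter.
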